7.1.2 E2007

E2007/perampanel is a first-in-class noncompetitive and highly selective α -amino-3-hydroxy-5-methyl-4-isoxazolepropionic acid (AMPA) receptor antagonist that was discovered and developed by Eisai.

Perampanel was approved for marketing as an adjunctive therapy for the treatment of POS with or without secondarily generalized seizures in patients aged 12 years and older in Europe and the United States in 2012, and in subsequently more than 59 countries. Perampanel was also approved for marketing as an adjunctive therapy for the treatment of PGTC seizures in patients

with epilepsy aged 12 years and older in Europe and the United States in 2015. In Japan, the above 2 indications were approved in March 2016. Furthermore, perampanel was approved for marketing as a monotherapy for the treatment of POS with or without secondarily generalized seizures in patients aged 12 years and older in the United States in 2017. In addition, Eisai applied for approval in the United States to expand the indications of adjunctive therapy for the treatment of POS with or without secondarily generalized seizures and PGTC seizures in patients aged 2 years and older in 2018.

Depending on the mechanism of action, existing antiepileptic drugs (AEDs) are divided into 2 groups, the first of which decrease neuronal excitation, and the second of which enhance inhibition. Major target sites for AEDs are blockage of voltage-operated sodium channels or calcium channels, regulation of neuronal transmitter release, inhibition of glutamatergic neural transmission, and facilitation of gamma-aminobutyric acid (GABA)-ergic neurotransmission. Current major AEDs are speculated to have a selective or mixed action on these targets. Perampanel is the only available drug showing noncompetitive and selective antagonism to AMPA receptors.

Further detailed information on perampanel including the data of the nonclinical and clinical studies that have been completed so far are provided in the Investigator's Brochure.

7.2 Study Rationale

In advance of this study, Eisai conducted a survey that aimed to investigate the needs of antiepileptic-injection use among epileptologists, and the results suggested that a need for antiepileptic-injection use exists for patients for whom it is temporarily not feasible to receive oral AEDs due to undergoing surgical procedures or other reasons.

Perampanel is the only available noncompetitive and selective AMPA receptor antagonist. For that reason, when patients cannot temporarily receive a safe and effective dose of oral perampanel, and are forced to switch to another oral AED, risks such as poor tolerability and seizure control are likely to result for the patients. Therefore, the development of a perampanel intravenous formulation to be used as an alternative to the oral formulation is significant.

Thus, conducting this study, which aims to evaluate the safety and tolerability, as well as the pharmacokinetics and efficacy of intravenous infusion of perampanel as a substitute for oral perampanel, is considered appropriate.

8. STUDY OBJECTIVES

8.1 Primary Objective

The primary objective of this study is to evaluate the safety and tolerability of 30-minute intravenous infusions of perampanel after switching from oral perampanel (8 to 12 mg/day) as an adjunctive therapy in subjects with POS with or without secondarily generalized seizures or PGTC seizures.

8.2 Secondary Objectives

The secondary objectives of this study are:

- To evaluate the plasma concentration of perampanel before and after switching from oral perampanel to 30-minute intravenous infusions of perampanel
- To evaluate the seizure frequency before and after switching from oral perampanel to 30-minute intravenous infusions of perampanel

9. INVESTIGATIONAL PLAN

9.1 Overall Study Design and Plan

This is a multicenter, uncontrolled, open-label study in subjects with POS with or without secondarily generalized seizures or PGTC seizures. This study will consist of 3 phases: the Pretreatment Phase, Treatment Phase, and Follow-up Phase.

During the Pretreatment Phase, 8 to 12 mg/day of oral perampanel will be administered. During the Treatment Phase, eligible subjects will be switched from oral perampanel on Day 1 to intravenous infusion of perampanel at a dose equivalent to the oral perampanel dose. Subjects will receive 30-minute intravenous infusions of perampanel once a day for 4 days under inpatient conditions. Afterwards, the subject must be switched back to oral perampanel at the equivalent daily dose of the intravenous infusion of perampanel. In addition, subjects must receive a stable dosage of 1 to a maximum of 3 marketed AED(s) throughout the study.

An overview of the study design is presented in Figure 1.

[figure not shown]

Figure 1 Study Design

9.1.1 Pretreatment Phase

The Pretreatment Phase is defined as the period from Day -28 to immediately before intravenous infusion of perampanel on Day 1. On any day from Day -28 to Day -7, informed consent/assent will be obtained from the subjects, and the subjects will be screened.

Subject informed consent/assent will be obtained before the screening, and protocol eligibility will subsequently be established. Eligible subjects must be on a stable dosage (8 to 12 mg/day) of oral perampanel as an adjunctive therapy with 1 to a maximum of 3 marketed concomitant AEDs for at least 28 days before the first dose of the study drug (ie, intravenous infusion of perampanel).

Eligible subjects will return to and remain onsite (be “hospitalized”) 1 day before switching

from oral perampanel to intravenous infusion of perampanel (ie, on Day –1 [Visit 2]).

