- Pretreatment Phase: Up to 29 days
- Treatment Phase: 4 days (the period beginning at the start of intravenous infusion of perampanel on Day 1 to immediately before the oral perampanel administration on Day 5)
- Follow-up Phase: Assessments at the Follow-up Visit will be conducted 7 days (allowance window: +7 days) after the last intravenous infusion of perampanel.

Concomitant Drug/Therapy

For at least 28 days before Day 1 in the Treatment Phase and throughout the study (or until the visit at the time of early discontinuation for discontinued subjects), subjects must be on a stable dosage of 1 to a maximum of 3 marketed concomitant AEDs.

Prohibited Concomitant Medications and Foods

For 14 days before Day 1 in the Treatment Phase and throughout the study (or until the visit at the time of early discontinuation for discontinued subjects), concomitant use of the following drugs and foods is prohibited.

- Other than carbamazepine and phenytoin, concomitant use of the following drugs or foods known to induce CYP3A (not limited to these):
enzalutamide, mitotane, phenobarbital (except for use as an AED), amobarbital, secobarbital, rifabutin, rifampicin, food containing St. John's Wort (*hypericum perforatum*), bosentan, efavirenz, etravirine, modafinil, aprepitant, echinacea, pioglitazone, vemurafenib, nevirapine, and glucocorticoids (except for topical use)

The use of the following drugs is prohibited within 28 days or approximately 5 half-lives of the previous investigational drug (whichever is longer) before Visit 1, as well as during the study (or until the visit at the time of early discontinuation for discontinued subjects).

- Other investigational drugs

The use of the following drug is prohibited during the Treatment Phase:

- Oral perampanel

Prohibited Concomitant Therapies

The following therapies must not be implemented during the study (or until the visit at the time of early discontinuation for discontinued subjects).

- Brain surgery
- Neuromodulation therapy except for VNS (transcranial magnetic stimulation, etc.)

The following therapies must not be implemented within 28 days before Visit 1, as well as throughout the study (or until the visit at the time of early discontinuation for discontinued subjects).

- Therapies with a medical device under clinical study

Restricted Concomitant Drugs

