9.1.2 Treatment Phase

The Treatment Phase is defined as the period beginning at the start of intravenous infusion of perampanel on Day 1 to immediately before the oral perampanel administration on Day 5.

Hospitalized subjects will be switched from oral perampanel on Day 1 to intravenous infusion of perampanel at a dose equivalent to the oral perampanel dose. Subjects will receive 30-minute intravenous infusions of perampanel once a day for 4 days under inpatient conditions (Days 1 through 4).

Subjects will be discharged from the hospital the day after the last intravenous infusion of perampanel (ie, Day 5), and treatment must be switched back to their original dose of oral perampanel.

If subjects cannot continue intravenous infusion of perampanel for any reason(s), they must discontinue the study.

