9.1.3 Follow-up Phase

The Follow-up Phase is defined as the period after switching back to oral perampanel administration.

The assessments at the Follow-up Visit will be conducted 7 days (allowance window: +7 days) after the last intravenous infusion of perampanel.

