9.5.1.5.1 ADVERSE EVENTS

An AE is any untoward medical occurrence in a clinical investigation subject administered an investigational product. An AE does not necessarily have a causal relationship with the

medicinal product. For this study, the study drug is perampanel intravenous formulation.

The criteria for identifying AEs in this study are:

- Any unfavorable and unintended sign (including an abnormal laboratory finding), symptom, or disease temporally associated with use of an investigational product, whether or not considered related to the investigational product (Note: Every sign or symptom should not be listed as a separate AE if the applicable disease [diagnosis] is being reported as an AE)
- Any new disease or exacerbation of an existing disease
- Any deterioration in nonprotocol-required measurements of a laboratory value or other clinical test (eg, ECG or x-ray) that results in symptoms, a change in treatment, or discontinuation of the study drug
- Recurrence of an intermittent medical condition (eg, headache) not present pretreatment
- An abnormal laboratory test result should be considered an AE if the identified laboratory abnormality leads to any type of intervention, withdrawal of the study drug, or withholding of the study drug, whether prescribed in the protocol or not.

All AEs, regardless of relationship to the study drug or procedure, should be recorded in the CRF beginning from the time the subject signs the study ICF through the last visit and for 21 days after the subject's last dose of the study drug. Serious AEs will be collected for 28 days after the last dose of the study drug. In addition, the start date and time of an adverse event, and the end date and time of the adverse event will be recorded in the CRF.

Abnormal laboratory values should not be listed as separate AEs if they are considered to be part of the clinical syndrome that is being reported as an AE. It is the responsibility of the investigator to review all laboratory findings in all subjects and determine if they constitute an AE. Medical and scientific judgment should be exercised in deciding whether an isolated laboratory abnormality should be classified as an AE. Any laboratory abnormality considered to constitute an AE should be reported on the CRF.

All events associated with suicidal ideation/attempt, regardless of severity, must be recorded as an AE in the CRF.

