9.5.1.5.3 STUDY-SPECIFIC ADVERSE EVENTS

In a non-clinical toxicity study of sodium sulphobutylether-beta-cyclodextrin (hereinafter “SBECD”), which is one of the additives in this study drug, vacuolation was observed in tubular epithelial cells, suggesting that patients with impaired renal function have a risk of SBECD accumulation (Luke, et al., 2010). In addition, there have been reports of anaphylaxis, possibly due to SBECD, with other formulations containing SBECD.

In this study, based on the above findings, adverse events associated with renal dysfunction, and adverse events associated with anaphylaxis will be handled as “adverse events of special interest (AESIs)” and recorded in the CRF.

For the procedures for reporting adverse events of special interest, see Section 9.5.4.3.2

1. Adverse Events Associated With Renal Dysfunction

If an adverse event associated with renal dysfunction occurs, and does not resolve at the time point when the Follow-up Phase is completed, the investigator will monitor the subject for 14 days from the follow-up visit, regardless of severity, and will continue following up the subject as needed until resolution of the event or, if resolution is unlikely, until stabilization of the symptom or sign. During this period, the subject will be followed up continuously by renal function monitoring at unscheduled visits (eg, once weekly, or at a frequency deemed necessary by the investigator).

2. Adverse Events Associated With Anaphylaxis

In the event of an adverse event associated with anaphylaxis, the investigator will take the following responsive actions:

- Take the first response, for example, by immediately referring the subject to an appropriate clinical department;
- Make a decision regarding whether or not to continue administration of the study drug to the subject, based on advice from the physician in the above-mentioned department;
- In the event of an adverse event associated with anaphylaxis while continuing intravenous administration of the study drug, discontinue the administration. In the event of any symptom or sign that is suspected of anaphylaxis while continuing intravenous administration of the study drug, careful judgment will be exercised in determining whether or not to continue the administration.

The follow-up of anaphylaxis will be continued until resolution of the event or, if resolution is unlikely, until stabilization of the symptom or sign.

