9.7.1.8.2 ADVERSE EVENTS

The AE verbatim descriptions (investigator terms from the CRF) will be classified into standardized medical terminology using the Medical Dictionary for Regulatory Activities (MedDRA). Adverse events will be coded to the MedDRA (Version 21.0 or higher) lowest level term (LLT) closest to the verbatim term. The linked MedDRA preferred term (PT) and primary system organ class (SOC) are also captured in the database.

A treatment-emergent adverse event (TEAE) is defined as an AE that emerges on or after the start of the study treatment, having been absent at pretreatment or

- Reemerges on or after the start of the study treatment, having been present at pretreatment but stopped before the start of the study treatment, or
- Worsens in severity on or after the start of the study treatment relative to the pretreatment state, when the AE is continuous.

All AEs, treatment-emergent or otherwise, will be presented in the subject data listings.

The incidences of TEAEs will be reported as the number (percentage) of subjects with TEAEs by SOC and PT. A subject will be counted only once within an SOC and PT,

even if the subject experienced more than 1 TEAE within a specific SOC and PT. The number (percentage) of subjects with TEAEs will also be summarized by maximum severity (mild, moderate, or severe).

The number (percentage) of subjects with treatment-related TEAEs will be summarized by SOC and PT. Treatment-related TEAEs include those events considered by the investigator to be related to the study treatment. The number (percentage) of subjects with treatment-related TEAEs will also be summarized by maximum severity (mild, moderate, or severe).

The number (percentage) of subjects with AEs by SOC and PT will be summarized by Phase (Pretreatment Phase, Treatment Phase, and Follow-up Phase) of onset.

Subject data listings of all AEs leading to death, all SAEs, and all AEs leading to discontinuation from the study will be provided.

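### AE percentages by phase of onset (9.7.1.8.2) compare observation windows of 7 to 28, 4 and about 20 days, so they partly measure window length

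*Protocol*

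**What the plan says.** Protocol 9.7.1.8.2 commits to a table in which "subjects with AEs by SOC and PT will be summarized by Phase (Pretreatment Phase, Treatment Phase, and Follow-up Phase) of onset". The entries are counts and percentages of subjects. The text attaches no measure of observation time.

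The three phases and the collection rules are set elsewhere:

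- **Pretreatment (9.1.1):** "The Pretreatment Phase is defined as the period from Day -28 to immediately before intravenous infusion of perampanel on Day 1". The next sentence of that section allows consent and screening on any day from Day -28 to Day -7. The synopsis gives the length as "Pretreatment Phase: Up to 29 days".
- **Treatment (9.1.2):** from the start of the Day 1 infusion "to immediately before the oral perampanel administration on Day 5".
- **Follow-up (9.1.3):** "The Follow-up Phase is defined as the period after switching back to oral perampanel administration". No end is given.
- **AE collection (9.5.1.5.1):** "beginning from the time the subject signs the study ICF through the last visit and for 21 days after" the last dose of study drug. Serious AEs are collected for 28 days after the last dose. Note f of Table 2 gives the same two limits.

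The treatment-emergent definition in 9.7.1.8.2 covers "an AE that emerges on or after the start of the study treatment" and states no end. Seizures, by contrast, are analysed per day in each phase (9.7.1.1).

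**The concern.** The primary objective (8.1) is the safety and tolerability of the infusion after a switch from the tablet, and there is no control group. The treatment-emergent tables mix the 4 intravenous days with all later oral days. The by-phase table is therefore where a reader will look to see how AEs on intravenous days compare with AEs on oral days.

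The percentage of subjects with at least one AE rises with the time they are watched. Here the intravenous window is the shortest of the three. With no change in daily risk, the infusion column would show the lowest percentage, and the table could be read as evidence of better tolerability than the tablet.

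**Working it through.** **Plan's own figures.** There is no Day 0. Day -28 to Day 1 counted inclusively is 28 + 1 = 29 calendar days, which reproduces the synopsis maximum (28 elapsed days). The start of Day 1 to Day 5 is 5 - 1 = 4 elapsed days, as stated for Treatment.

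**Observed AE windows, in elapsed days, for a subject who receives all four infusions (last on Day 4).**

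| Phase | Start of AE observation | End | Days |
|---|---|---|---|
| Pretreatment | consent, Day -28 to Day -7 | infusion on Day 1 | 28 to 7 |
| Treatment | infusion on Day 1 | oral dose on Day 5 | 4 |
| Follow-up, AEs | Day 5 | Day 4 + 21 = Day 25 | 25 - 5 = 20 |
| Follow-up, serious AEs | Day 5 | Day 4 + 28 = Day 32 | 32 - 5 = 27 |

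From Day 1 to Day 25 there are 24 days, of which 4 are intravenous: 4/24 = 17% of the time pooled in the treatment-emergent tables (non-serious AEs).

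With 20 completers, the subject-days are:
- Pretreatment: 20 × 7 = 140 to 20 × 28 = 560
- Treatment: 20 × 4 = 80
- Follow-up (AEs): 20 × 20 = 400

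**Effect of window length alone.** The protocol gives no AE rate, so the 4-day incidence p is assumed at three values, with a constant daily risk. The proportion of subjects with at least one AE in d days is then P(d) = 1 - (1 - p)^(d/4).

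| p over 4 days | Pretreatment, d = 7 | Pretreatment, d = 28 | Follow-up, d = 20 |
|---|---|---|---|
| 5% | 8.6% | 30.2% | 22.6% |
| 10% | 16.8% | 52.2% | 41.0% |
| 20% | 32.3% | 79.0% | 67.2% |

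For example, with p = 10% and d = 20: 1 - 0.9^5 = 41.0%. In 20 subjects the 10% row is 2 subjects in Treatment, 3.4 to 10.4 in Pretreatment and 8.2 in Follow-up, with no true difference. The two Pretreatment columns are the extremes, with all subjects consenting on Day -7 or all on Day -28. A real sample lies between them.

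Under the same model, Treatment and Follow-up show equal percentages only if the daily risk on intravenous days is 20/4 = 5 times the Follow-up risk. Against Pretreatment the factor is 7/4 = 1.75 to 28/4 = 7.

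**Precision of a rate for Treatment.** Two onsets in 80 subject-days is 2/80 × 100 = 2.5 per 100 days. The exact Poisson limits for 2 events are 0.242 and 7.225. Dividing by 80 and multiplying by 100 gives 0.3 to 9.0.

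**The case against.** The strongest reply has four parts.

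- **No comparison is planned.** The before-and-after objectives in 8.2 concern plasma concentration and seizures, not AEs. This stands: no test or decision depends on the table, which limits the weight of the point.
- **The listings show onset.** All AEs are listed, with start date and time recorded, and 20 subjects can be read case by case. That helps a careful reader, but it does not change what the summary table shows.
- **The statistical analysis plan may add rates.** It may, and it is not shown. The percentage by phase is nevertheless stated in the protocol, and so are the phase definitions it uses.
- **The size rests on assumptions.** It does: constant daily risk and assumed incidences. Closer inpatient observation could raise AE reporting on intravenous days and offset the effect in part or in full.

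Three stronger readings are tempting, and the documents do not support them.

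1. A reader might infer that AEs starting after the Follow-up Visit belong to no phase, so that Follow-up lasts only 6 to 13 days (Day 5 to a visit on Day 11 to 18). This comes from 9.5.1.5.3, where "when the Follow-up Phase is completed, the investigator will monitor the subject for 14 days from the follow-up visit" reads as if the phase ends at that visit. That passage is an instruction on monitoring renal events, not a phase definition. Sections 9.1.3 and 9.5.1.5.1 read together give about 20 days for AEs.
2. A reader might infer that the Day -28 start in 9.1.1 puts AEs in the wrong phase. It moves none. Every AE recorded before the first infusion is in Pretreatment, whether the phase starts on Day -28 or at consent, and the percentage base is subjects. The start date matters only once days are counted.
3. A reader might infer that the trial will conclude that the infusion is safer than the tablet. Nothing in the protocol plans that conclusion.

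**Conclusion.** The concern holds in a limited form, and it is minor. The by-phase percentages in 9.7.1.8.2 cover observed windows of 7 to 28, 4 and about 20 days (about 27 for serious AEs). They cannot be compared across phases as they stand. At equal daily risk, 10% in Treatment corresponds to 17% to 52% in Pretreatment and 41% in Follow-up, which favours the infusion through window length alone. These figures assume subjects who complete treatment, a constant daily risk and an incidence that the protocol does not give. The net direction in practice is uncertain, because inpatient observation may work the other way. The missing end of Follow-up in 9.1.3 should be settled at the same time, because an AE rate needs a stated number of days.

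**What to change.** 1. **9.7.1.8.2, by-phase table:** beside the count and percentage, show for each phase the subject-days of AE observation and the AE onsets per 100 subject-days. Count Pretreatment days from consent, not from Day -28.
2. **9.1.3:** state an end of the Follow-up Phase for AE analysis that matches collection, namely 21 days after the last infusion. Keep serious AEs that start after that point and up to 28 days in Follow-up, but show them separately and leave them out of the rate, because non-serious AEs are no longer collected then.
3. **9.5.1.5.3:** reconcile the wording that implies the phase ends at the Follow-up Visit with 9.1.3. This concerns only the name of the period, not the monitoring itself.

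The cost is wording in three sections and extra columns in one table. No new data are needed: consent is obtained at Visit 1, and infusion times (9.4.1) and AE start times (9.5.1.5.1) are already recorded. The drawback is an imprecise Treatment rate. Two onsets in 80 subject-days would give 2.5 per 100 days with an exact 95% interval of 0.3 to 9.0, so the rates should be presented as descriptive.
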